**If you answered “no” to Question 52 above, was your child's activity limited by: (Circle yes to all that apply)**

	Yes
53. Pain?	1
54. General Health?	1
55. Doctor or parent instructions?	1
56. Fear the other kids won't like him/her?	1
57. Dislike of pickup games or sports?	1
58. Too young?	1
59. Activity not in season?	1

**60.** How often in the **last week** did your child get together and do things with friends? (Circle one response.)

- 1 Often                                      2 Sometimes                                      3 Never or rarely

**If you answered “sometimes” or “never or rarely” to Question 60 above, was your child's activity limited by: (Circle yes to all that apply)**

	Yes
61. Pain?	1
62. General Health?	1
63. Doctor or parent instructions?	1
64. Fear the other kids won't like him/her?	1
65. Friends not around?	1

**66.** How often in the **last week** did your child participate in **gym/recess**? (Circle one response.)

- 1 Often                                      2 Sometimes                                      3 Never or rarely                                      4 No gym or recess

**If you answered “sometimes” or “never or rarely” to Question 66 above, was your child's activity limited by: (Circle yes to all that apply)**

	Yes
67. Pain?	1
68. General Health?	1
69. Doctor or parent instructions?	1
70. Fear the other kids won't like him/her?	1
71. Dislike of gym/recess?	1
72. School not in session?	1
73. Does not attend school?	1

74. Is it easy or hard for your child to make friends with children his/her own age? (Circle one response.)

- 1 Usually easy      2 Sometimes easy      3 Sometimes hard      4 Usually hard

75. How much pain has your child had during the **last week**? (Circle one response.)

- 1 None      2 Very mild      3 Mild      4 Moderate      5 Severe      6 Very severe

76. During the **last week**, how much did pain interfere with your child's normal activities (including at home, outside of the home, and at school)? (Circle one response.)

- 1 Not at all      2 A little bit      3 Moderately      4 Quite a bit      5 Extremely

What expectations do you have for your child's treatment?  
 As a result of my child's treatment, I expect my child:  
 (Circle one response on each line.)

	Definitely yes	Probably yes	Not sure	Probably not	Definitely not
77. To have pain relief.	1	2	3	4	5
78. To look better.	1	2	3	4	5
79. To feel better about himself/herself.	1	2	3	4	5
80. To sleep more comfortably.	1	2	3	4	5
81. To be able to do activities at home.	1	2	3	4	5
82. To be able to do more at school.	1	2	3	4	5
83. To be able to do more play or recreational activities (biking, walking, doing things with friends).	1	2	3	4	5
84. To be able to do more sports.	1	2	3	4	5
85. To be free from pain or disability as an adult.	1	2	3	4	5

86. If your child had to spend the rest of his/her life with his/her bone and muscle condition **as it is right now**, how would you feel about it? (Circle one response.)

- 1 Very satisfied      2 Somewhat satisfied      3 Neutral      4 Somewhat dissatisfied      5 Very dissatisfied

## 1. VERSION HISTORY

Version 5 of the Statistical Analysis Plan (SAP) for study B5161002 specified more details of the thigh MRI endpoints and the analyses, including the analysis to evaluate predictive relationship between the thigh MRI endpoints and the primary endpoint 4SC time. It also made a few clarifications and added an additional sensitivity analysis for the primary endpoint.

Version 4 of the Statistical Analysis Plan (SAP) for study B5161002 updated the baseline requirement for the subgroup analysis involved in the tier-2 of the interim analysis.

Version 3 of the Statistical Analysis Plan (SAP) for study B5161002 incorporates the expanded interim analysis decision criteria.

Version 2 of the Statistical Analysis Plan (SAP) for study B5161002 is based on the protocol dated 15 AUG2016 (Amendment 2). The SAP was revised to reflect the changes in the revised protocol.

SAP Version	Change	Rationale
1	Not Applicable	Original SAP
2	
In Section 2.1.2, two secondary objectives and endpoints have been added.
 
S6: To characterize the long-term effects following approximately 2-years of treatment with PF-06252616 on functional assessments compared to historical control.
 
S7: To characterize the effects of PF-06252616 on muscle strength and functional assessments compared to placebo in subset of subjects who may demonstrate a rapid disease decline and with relatively low variability over a one-year period (see Section 6.4 for the
	
 
The first objective was added to further describe how data from Sequence group 1 (subjects who will receive PF-06252616 in both Period 1 and 2 for approximately 2 years) will be evaluated for long-term efficacy. Upon review of additional Duchenne muscular dystrophy (DMD) natural history data of the 4 stair climb (4SC) which recently became available from 4 separate studies (The Cooperative International Neuromuscular Research Group [CINRG], University of Cincinnati [UofCCNT], University of Florida [UofFLA] and Leuven), the mean change in 4SC observed over 1 year was less (ranging from 0.9 to 1.99 seconds) in DMD patients who are 6 to <10 years old with a baseline 4SC of 2.5 to 12 seconds than originally estimated (~2.9 seconds) from the data available at the time when the protocol was first written. In addition, the natural history data showed that the 4SC time change over two years is approximately 4.3 seconds on average (in DMD patients who are 6 to <10 years old with a baseline 4SC of 2.5 to 12 seconds).
 

090177e1909dd632\Approved\Approved On: 25-Mar-2019 05:54 (GMT)

	definition of the subset).	
Because the placebo arm in the study is only for 1 year (during period 1 in Sequence group 3) the plan is to review the functional data as compared to a matched historical control group.
 
 
The second objective will allow for an analysis in a subset of subjects who may be more likely to decline in one-year who also may have less variability, as determined by their baseline data. This subset is being proposed following a review of additional natural history data which was not available at the time of the initial study design. As additional natural history data are obtained 4SC baseline values which predict patients who are more likely to decline in one year with less variability will be evaluated.
 

2	In CCI the decision boundaries for the interim analysis have been updated.	
 
CCI
 

2	
In Section 3.2 and Section 6.2:
 
Endpoints were updated to describe the data that will be used to evaluate the two new secondary objectives.
 
Corrections were made to time points for endpoints.
 
Removed strength testing by Medical Research Council (MRC) Scale to reduce the burden of testing on subjects.
	Reflect the corresponding changes made in the revised protocol.
2	In Section 5.3 , added additional sensitivity analyses.	Resulted from discussions with regulatory authorities.

090177e1909dd632\Approved\Approved On: 25-Mar-2019 05:54 (GMT)

2	In Section 3.3.1, 3.3.2, 6.3.1, and 6.3.2, updated PK and PD endpoints and analysis.	Based on planned PK/PD data collection schedule and data availability.
2	In Section 6.4, added a subset analysis.	Reflect the changes made in the revised protocol.
3	In Section 7.1 and CCI	Reflect the changes in the interim analysis decision criteria.
4	In CCI	CCI
5	In Section 3.2, 3.3, 6.2, and 6.4.	Clarified endpoint details including the pre-specified subsets, the timed function tests within the NSAA endpoint, and the PODCI score.
5	In Section 3.5.	Clarified the AE Tier-2 event definition to align with the “Rule of 4” given the trial will have less than 400 or fewer subjects per treatment group, and clarified the AE Tier-3 event analysis.
5	In Section 6.1.	Added a summary plot of the cumulative percent of patients with a percent change from baseline on 4SC time less than a given set of thresholds as an additional sensitivity analysis.
5	In Section 3.3, 6.2, 6.3, and 6.4.	Specified more details of the thigh MRI endpoints and the analyses; included the analysis to evaluate predictive relationship between the thigh MRI endpoints and the primary endpoint 4SC time.
5	In CCI	CCI

**2. INTRODUCTION**

Note: in this document any text taken directly from the protocol is *italicized*.

This SAP provides the detailed methodology for summary and statistical analyses of the data collected in study B5161002. This document may modify the plans outlined in the protocol; however, any major modifications of the primary endpoint definition or its analysis will also be reflected in a protocol amendment.

090177e1909dd632\Approved\Approved On: 25-Mar-2019 05:54 (GMT)

## 2.1. Study Objectives

### 2.1.1. Primary Safety and Efficacy

- **P1:** To determine the safety and tolerability of multiple ascending repeat IV doses of PF-06252616 in ambulatory boys with DMD.
- **P2:** To demonstrate the efficacy of treatment with IV doses of PF-06252616 based on an observed mean change from baseline on function (4 Stair Climb) as compared to placebo following 49 weeks of treatment.

### 2.1.2. Secondary

- **S1:** To characterize the effects of PF-06252616 on muscle strength and other functional assessments compared to placebo.
- **S2:** To evaluate the PD activity of PF-06252616 based on the percent change of muscle volume from baseline as compared to placebo.
- **S3:** To evaluate the PD profile of PF-06252616 based on GDF-8 (myostatin) modulation in blood.
- **S4:** To characterize the PK profile of PF-06252616.
- **S5:** To evaluate the immunogenicity of PF-06252616.
- **S6:** To characterize the long-term effects following approximately 2-years of treatment with PF-06252616 on functional assessments compared to historical control (see [Section 6.2.1](#)).
- **S7:** To characterize the effects of PF-06252616 on muscle strength and functional assessments compared to placebo in a subset of subjects who may demonstrate a rapid disease decline and with relatively low variability over a one-year period (see [Section 6.4](#)).

### 1.1.1. Exploratory

- **E1:** To evaluate biomarkers that may be informative in demonstrating the pharmacologic effect of PF-06252616.
- **E2:** To evaluate biomarkers that may be informative for monitoring hepatic liver injury in the setting of dystrophic muscle.
- **E3:** To evaluate the Functional Health Status.
- **E4:** To evaluate long term safety of PF-06252616 in subjects treated for >1 year.
- **E5:** To evaluate duration of treatment response following withdrawal and/or continuation of treatment for >1 year.

- **E6:** To evaluate response in a delayed treatment group (Sequence Group 3, Period 2).

## 2.2. Study Design

*This is a Phase 2 randomized, 2-period, double-blind, placebo-controlled, multiple ascending dose study to evaluate the safety, efficacy, PK and PD of PF-06252616 administered to ambulatory boys diagnosed with DMD. Three IV infused dose levels (5, 20 and 40 mg/kg) administered every 28 days will be investigated in a within subject dose escalating fashion.*

*Approximately 105 eligible subjects will be randomly assigned to 1 of 3 sequence groups and receive investigational product for approximately 96 weeks (2 treatment periods of approximately 48 weeks each) stratified by their baseline time to complete the 4 stair climb (either  $\leq$  or  $>8$  seconds).*

### **Sequence 1 (n=35):**

*Period 1: Active treatment (PF-06252616) within subject dose escalation (5, 20 and 40 mg/kg)*

*Period 2: Active treatment (PF-06252616) at the maximum tolerated dose in Period 1*

### **Sequence 2 (n=35):**

*Period 1: Active treatment (PF-06252616) within subject dose escalation (5, 20 and 40 mg/kg)*

*Period 2: Placebo*

### **Sequence 3 (n=35):**

[figure not shown]
*Period 1: Placebo*

*Period 2: Active treatment (PF-06252616) within subject dose escalation (5, 20 and 40 mg/kg)*

*Each dose level will be explored in a dose escalating fashion within subjects, starting with the lowest dose. At each dose level, dosing will be administered over a 2-hour IV infusion every 4 weeks for a total of 16 weeks (4 doses). Dose escalation within a subject will occur following the planned fourth dose within each dose level. Subjects will move from Period 1 to Period 2 without a pause between periods.*

The following is a schematic of the study design.

**Figure 1. Study Schematic**

Note: Sequence 1, Period 2 demonstrates subjects continuing on the maximum tolerated dose.  
 SCRIN=Screening, PBO=Placebo

**2.3. Process 1 and Process 2 Material**

With the progression of the clinical development activities for PF-06252616, the current manufacturing process of PF-06252616 (referred to as Process 1) has been modified to a commercial-ready process (referred to as Process 2). Process 2 has improved productivity to meet commercial needs, but without change to the substance formulation. Changes from Process 1 and Process 2 include:

- Transition from the PF-06252616 100 mg/vial to a 260 mg/vial;
- Utilization of ½ the volume for reconstitution, while keeping post-reconstitution formulation identical.

The plan for introduction of Process 2 in this study is as follows and is dependent on individual subject status once Process 2 material becomes available:

- Any subject who receive Process 1 material will remain on Process 1 material throughout Period 1, but may be switched to Process 2 during Period 2. However, once Process 1 are depleted, Process 2 will be dispensed in Period 1 as well.
- Once a subject receives Process 2 material, he will only receive Process 2 material throughout remainder of participation.

Pharmacokinetic, pharmacodynamics and immunogenicity analyses will be performed in this study so as to confirm comparability of Process 1 and Process 2 materials, as further described in Section 6.3.1.3.2, 6.3.2.2, and 6.6.7, respectively.

090177e1909dd632\Approved\Approved On: 25-Mar-2019 05:54 (GMT)

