**Table 1. PK Parameters To Be Determined**

Subjects	Visit(s)	Parameter	Analysis Scale	PF-06252616
All Subjects	Weeks 13, 29, 45, 61, 77, 93 (Last dose for each dose escalation level in Periods 1 and 2) (Period 1 and Period 2)	$C_{trough}$	ln	D
		$C_2$	ln	D
Subjects in Sequence 2	Week 45 (Last dose in Period 1)	$t_{1/2}^a$	R	D
Subjects with additional PK sampling	Weeks 1, 13, 17, 29, 33, 45 (First and last dose for each dose escalation level in Period 1)	$C_{max}$	ln	D
		$T_{max}$	R	D
		$AUC_{\tau}$	ln	D
		$C_{av}$	ln	D
	Weeks 13, 29, 45 (Last dose for each dose escalation level in Period 1)	$CL$	ln	D
Subjects in Sequence 2 with additional PK sampling	Week 45 (Last dose in Period 1)	$V_{ss}^a$	ln	D

- Key: D = Displayed with descriptive statistics, ln = natural log transformed, R=raw (untransformed), a = if data permits.

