**6.3.1.3.2. Analysis of Pharmacokinetic Parameters**

If a PK parameter cannot be derived from a subject’s concentration data, the parameter will be coded as NC (ie, not calculated). (Note that NC values will not be generated beyond the day that a subject discontinues.)

In summary tables, statistics will be calculated by setting NC values to missing; and statistics will not be presented for a particular treatment if more than 50% of the data are NC.

If an individual subject has a known biased estimate of a PK parameter (due for example to an unexpected event such as incomplete administration of the IV infusion dose), this will be footnoted in summary tables and will not be included in the calculation of summary statistics.

*The PK parameters will be listed and summarized for subjects in the PK parameter analysis set. Parameters will be summarized by sequence, visit, and dose.*

*Each PK parameter will include the set of summary statistics as specified in the table below:*

Parameter	Summary Statistics
Cmax, AUCτ, Cav, Ctrough, CL, Vss, C2	N, arithmetic mean, median, cv%, standard deviation, minimum, maximum, geometric mean, geometric CV%
t1/2	N, arithmetic mean, median, cv%, standard deviation, minimum, maximum
Tmax	N, median, minimum, maximum

The following PK parameter summaries will be presented:

- All subjects (including those with additional PK sampling): Ctrough, C2, and for subjects in Sequence 2, also t1/2.
- Subjects with additional PK sampling: Ctrough, C2, Cmax, Tmax, AUCτ, Cav, CL, and for subjects in Sequence 2, also t1/2 and Vss.

Note Ctrough, C2, and t1/2 will be included in both summaries for the respective subject groups. Supporting data from the estimation of t1/2 will be listed for subjects in Sequence 2: the terminal phase rate constant (kel), goodness of fit statistic from the log-linear regression (r), and the first, last, and number of time points used in the estimation of kel.

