Ctrough and C2 for the last dose of each dose escalation level will be summarized for Process 1 and Process 2 material as shown in the following table. For Process 1 material, these PK parameters will be obtained in Period 1. For Process 2 material, these PK parameters will be obtained from patients who received placebo in Period 1 and receive Process 2 material for the first time in Period 2.

090177e1909dd632\Approved\Approved On: 25-Mar-2019 05:54 (GMT)

Dose	Process 1 Data: Sequences 1 and 2 Period 1	Process 2 Data: Sequence 3 Period 2
5 mg	Week 13	Week 61
20 mg	Week 29	Week 77
40 mg	Week 45	Week 93

Only subjects with at least 4 consecutive doses of Process 2 material will be included in the Process 2 summaries.

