#### **6.3.2.2. GDF-8 Parameters**

If a GDF-8 parameter cannot be derived from a subject's concentration data, the parameter will be coded as NC (ie not calculated). (Note that NC values will not be generated beyond the day that a subject discontinues).

In summary tables, statistics will be calculated by setting NC values to missing; and statistics will not be presented for a particular treatment if more than 50% of the data are NC. For statistical analyses (ie analysis of variance), GDF-8 parameters coded as NC will also be set to missing.

To assess the relationship between the GDF-8 trough concentrations and dose,  $C_{\text{trough(GDF-8)}}$  after last dose at each dose level will be plotted against dose, and will include individual subject values and the medians for each dose level. Medians will have a different symbol

than the individual values. A footnote will be added to the plots to indicate that medians are presented on the plot.

$C_{\text{trough(GDF-8)}}$  for the last dose of each dose escalation level will be summarized for Process 1 and Process 2 material as described above for PK.

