#### **6.6.7. Immunogenicity**

Immunogenicity analysis will be based on the immunogenicity analysis population which will be the same as the safety analysis population and will include anti-drug antibody and neutralizing antibody development by Week 97 and until the end of follow-up. Both continuous endpoints (titer) and categorical endpoints (ie, positive, negative and inconclusive) will be reported for the anti-drug antibody and neutralizing antibody assays by dose and sampling time points. Data permitting, the incidence of anti-drug antibody and

neutralizing antibody will be summarized by time points within each dose cohort, sequence, and may be also summarized by dose. The impact of anti-drug antibody and neutralizing antibody on PK and PD parameters and profiles, efficacy and safety may be also evaluated but no statistical inference will be drawn.

The immunogenicity of Process 1 material may be assessed from Sequence 1 and 2 for Period 1, and Sequence 2 of Period 2. To assess the immunogenicity of PF-06252616 Process 2 material, it is necessary that the subjects did not receive any prior administration of PF-06252616 Process 1 material. This may be obtained from subjects in Sequence 3 who received Placebo in Period 1 and receive drug product for the first time as Process 2 material in Period 2.

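### The SAP says its analyses will confirm that Process 1 and Process 2 material are comparable, but it plans only separate descriptive summaries, with no between-process estimate or interval

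*SAP*

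**What the plan says.** SAP 2.3 describes a change of manufacturing process during the study and states the aim: "analyses will be performed in this study so as to confirm comparability of Process 1 and Process 2 materials". It sends the reader to three sections for the method.

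- **PK, SAP 6.3.1.3.2.** C_trough and C2 at the last dose of each level "will be summarized for Process 1 and Process 2 material as shown in the following table". The table sets Sequences 1 and 2 in Period 1 (Process 1) beside Sequence 3 in Period 2 (Process 2). The statistics are one-group statistics: "N, arithmetic mean, median, cv%, standard deviation, minimum, maximum, geometric mean, geometric CV". The key to SAP Table 1 gives the code used for every parameter: "D = Displayed with descriptive statistics".
- **PD, SAP 6.3.2.2.** The GDF-8 trough "will be summarized for Process 1 and Process 2 material as described above for PK".
- **Immunogenicity, SAP 6.6.7.** Process 1 may be assessed from Sequences 1 and 2. For the other material: "To assess the immunogenicity of PF-06252616 Process 2 material, it is necessary that the subjects did not receive any prior administration" of Process 1, so those data may come from Sequence 3 in Period 2. No contrast between the two is described.

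SAP 6.3.1.3.2 also restricts the Process 2 summaries to boys with at least four consecutive Process 2 doses. SAP 2.3 allows Process 2 to be given in Period 1 once Process 1 stock runs out.

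**The concern.** Confirming comparability is a claim about how large the difference between two materials could be. It needs an estimate of that difference, a measure of its uncertainty, and a limit to judge it against. The plan supplies none of these. A reader of the output would have two columns of summary statistics and would have to judge by eye whether they are close enough.

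At stake is a subsidiary statement about the newer material. If the clinical study report calls the processes comparable, nothing in the planned tables will show how large a difference in exposure, GDF-8 trough or antibody incidence remains compatible with the data.

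**Working it through.** **Step 1: is a comparison planned anywhere?** SAP 6.3.1.3.2 gives one-group statistics by process. SAP 6.3.2.2 repeats that for GDF-8. Its mention of analysis of variance only says how non-calculable values are handled; no model, factor or process contrast is given. SAP 6.6.7 describes each process separately and conditionally. The process text in these sections is readable, so redaction does not explain the gap. The documents give no margin, confidence level, power or sample size for this comparison, so there is no figure to reproduce.

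**Step 2: group sizes.** From SAP 2.2, Process 1 has at most 35 + 35 = 70 boys and Process 2 at most 35. Applying the 10% attrition of Protocol 9.1: 0.9 × 70 = 63 and 0.9 × 35 = 31.5, taken as 31. That attrition was assumed for Week 49, and the Process 2 data come from Weeks 61 to 93, so 31 may be generous. Stock timing and the four-dose rule can lower it further; 10 is taken as a low case (assumption).

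**Step 3: precision of the missing estimate.** The CV of 30-50% is an assumption. On the ln scale, SD = √ln(1 + CV²), SE = SD × √(1/63 + 1/n₂), and the 90% interval around an observed ratio of 1 is exp(± t₀.₉₅ × SE).

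Example, CV 40%, n₂ = 31: SD = √ln(1.16) = 0.385; SE = 0.385 × √(1/63 + 1/31) = 0.0845; t = 1.662 on 92 df; factor exp(0.1404) = 1.15.

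| Process 2 boys | CV 30% | CV 40% | CV 50% |
|---|---|---|---|
| 31 | 0.90-1.11 | 0.87-1.15 | 0.84-1.19 |
| 10 | 0.85-1.18 | 0.80-1.24 | 0.76-1.31 |

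**Step 4: what a comparison by eye can tell.** Suppose a reader calls the materials alike when the ratio of geometric means lies between 0.85 and 1/0.85 (an illustrative rule, not in the SAP). The chance of that is:

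| | 31 boys, CV 30% | 10 boys, CV 50% |
|---|---|---|
| Materials identical | 99% | 69% |
| Process 2 exposure truly 20% lower | 17% | 35% |

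As the group shrinks, both answers become less reliable.

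**Step 5: would a formal margin work?** Take 80-125% as an example limit. With identical materials and 31 boys, one 90% interval falls inside it 93%, 67% or 38% of the time (CV 30, 40, 50%). Two PK parameters at three doses make six intervals. If all six must pass and were independent, the chances are 0.929⁶ ≈ 64%, 0.672⁶ ≈ 9% and 0.377⁶ < 1%. With a correlation of 0.8 they are about 81%, 34% and under 4%.

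**Step 6: antibodies.** The only ADA rate in the documents is 11.3% (6/53, healthy adults, Protocol 1.8.2). With 8/70 and 4/35 positive (both 11.4%), the Newcombe 95% interval for the difference is -11.8 to +15.5 percentage points. A doubling, +11.3 points, lies inside it.

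**The case against.** The strongest reply is that this is a descriptive, subsidiary analysis introduced by one over-strong verb. Process comparability is not among the primary, secondary or exploratory objectives, and no dosing, stopping or efficacy decision depends on it. SAP 2.3 says the formulation after reconstitution is unchanged. N, geometric mean and geometric CV are tabulated by group, so a reader could work out a ratio and an interval. Most of this stands and limits the weight of the point. It does not make the stated aim and the stated method agree, and an interval left to the reader is not one the plan commits to report or interpret.

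A reader might also infer that a smaller, noisier Process 2 group makes it easier to conclude that the materials are comparable. That would follow if a non-significant test were read as equivalence, but the SAP plans no test. Step 4 shows that noise also creates apparent differences between identical materials: the comparison becomes uninformative in both directions.

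A reader might likewise quote miss rates. With exposure truly 20% lower, a two-sided 5% t-test misses it 7%, 26% or 43% of the time with 31 boys, and 40%, 61% or 72% with 10 (CV 30, 40, 50%). Fisher's exact test misses a doubling of ADA from 11.3% in 75% (63 against 31) or 84% (63 against 10). These figures recompute, but they belong to tests that the SAP does not contain, and they rest on assumed inputs.

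**Conclusion.** The point holds as a mismatch between aim and method: the planned summaries contain no between-process estimate and no uncertainty, so they cannot confirm comparability. A short addition to the SAP would resolve it.

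Its size depends on CVs and Process 2 numbers that the documents do not give. Under the assumed ranges, the 90% interval for a PK ratio would be useful at 31 boys and low CV (0.90-1.11) and wide at 10 boys and high CV (0.76-1.31). For PK the gap may therefore lie in the plan more than in the data. For antibodies, even the full groups could not exclude a doubling.

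A reader might infer that the conclusion is needed to carry the Process 1 results over to commercial supply. The documents do not say so. Nor would an interval isolate the effect of process: boys are not randomised to process, and process is confounded with sequence and period.

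**What to change.** - **SAP 6.3.1.3.2 and 6.3.2.2:** at each dose level, add the Process 2/Process 1 ratio of geometric means with a 90% CI for C_trough, C2 and the GDF-8 trough, from the ln-scale data already planned. Group boys by the process actually received, because Process 2 may be dispensed in Period 1.
- **SAP 6.6.7:** add the difference in ADA incidence with a 95% CI. SAP 6.6.1 already plans risk differences with intervals for adverse events, so this fits existing practice.
- **SAP 2.3:** change the aim to estimating the difference between the two materials. The present claim could stay for PK only if the sponsor fixes and justifies a margin before unblinding, and states which parameters and dose levels must meet it.
- **SAP 2.3 or the table footnotes:** state that the comparison is non-randomised and confounded with sequence and period.

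The cost is SAP wording and one extra table from data already collected. The downside is that the result may have to be reported as inconclusive, even with about 31 Process 2 boys.
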